Title

Efficacy of Philips Sonicare Flexcare Platinum Toothbrush® compared to manual brushing in healthy patients: a 12 mouth randomized clinical trial.

Author

Introduction

Professional oral hygiene has become a customary procedure in everyday dentistry. Both manual and sonic brushes are part of normal oral hygiene education practice. The aim is the removal of biofilm, plaque and calculus from the dental surface. Routine recalls ensure a better oral health and greater protection against caries, gingivitis and periodontitis. Regular attendance to oral hygiene sessions plays an important role but has to be accompanied by the compliance with home oral care instructions. The patients should be adequately instructed to take care of their oral health. Compared with manual toothbrushes, ergonomic instruments, such as sonic toothbrushes, can be a more practical and less demanding mean to remove biofilm and plaque efficiently. Studies in literature investigate the efficacy of toothbrushes in plaque removal, but our study would validate efficacy of toothbrushes post-causal therapy, towards lower plaque accumulation, and reduction in bleeding.

Aim

The objective of this study is to compare two methods (manual VS sonic) of tooth brushing in terms of impact on the gingival index and plaque index after one session of Full Mouth-Erythritol Powder Air Polishing Therapy (FM-EPAPT) in healthy patients.

Materials and Methods

Trial design:

Monocetric, pragmatic, single blinded, randomized clinical trial (RCT) of parallel design. The trial will have one-year duration.

Participants:

Healthy subject affected by gingivitis are included in the study. The patients are treated at the Department of Surgical Specialties, Radiological Science and Public Health, School of Dentistry, Section of Periodontics, Brescia, Italy between the period 01/10/2017 -

01/10/2019. Presence of gingivitis is defined as bleeding on probing (BOP) > 25%.

Inclusion criteria are:

- Patients affected by gingivitis is defined as bleeding on probing (BOP) > 25%.
- Healthy young patients (18-40 years)
- Patients with almost 5 teeth per quadrant
- Patients smoking less than 10 cigarettes a day

Exclusion criteria are:

- Presence of periodontitis (pocket depth PPD > 4 mm)
- Patient with BOP and/or plaque index < 25%
- Patient with any systemic disease
- Orthodontic or prosthesis patient
- Patient with split
- Impossibility to come to the recall appointments
- Not willing to follow the agreed protocol

A written informed consent will be obtained from each patient included after explanation of the risks and benefits of participating in this study. No change in the trial design will be made after approval of the Ethics Committee.

Intervention

Age, sex, smoking habits should be recorded. At Baseline examination taken by (RA) the following periodontal index will be recorded at 6 sites per tooth.

- **P.P.D**: measured from the gingival margin to the bottom of the pocket.
- G.I. recorded as presence or absence of bleeding after gently run on the surface of the

marginal gingiva.

- **PI**: recorded as presence or absence of plaque. A probe will gently run on the surface of the teeth.
- **REC:** measured from the cement-enamel junction to the gingival margin.
- CAL: measured clinically from the base of the pocket to the cement-enamel junction

A PCP-UNC 15 periodontal probe is used on six sites per tooth (mesio-buccal, buccal, distobuccal, mesio-lingual, lingual and disto-lingual) with a gentle probing force by the same examiner. Measurements are rounded to the nearest millimetre.

Examiner calibration:

The examiner should be calibrated measuring PPD and PAL in one quadrant with at least 6 teeth on 10 patients. Measurements should be repeated after one hour and variability should be assessed

After baseline recording (RA), a professional oral hygiene (full mouth erythritol powder air polishing therapy – FM-EPAPT) will be done by VB.

After ultrasonic debridment the randomization envelope will be open by VB.

Group A: sonic toothbrush (Philips Sonicare Flexcare Platinum Toothbrush®) will be given

Group B: Manual brushing (Technique Pro - GUM® Sunstar Italiana SRL) will be given.

For each group specific instruction of oral hygiene will be done.

For all patient are recommended: toothbrush Hydral Gum (GUM® Sunstar Italiana SRL) and interdental floss (GUM® Sunstar Italiana SRL)

Each patient is recalled at 2 and 4 weeks to reinforce oral hygiene instructions (VB) and do collect GI and PI (RA).

Furthermore, all patients are recalled at 6 weeks 6 and 12 months for update of periodontal folder (RA); at 6 and 12 months professional hygiene will be done by VB.

At the end of the therapy reinforcement of oral hygiene instruction are given by VB.

Primary Outocome:

Change in P.I.. change in 10% of the site in test group.

Secondary Outcomes:

**Change in G.I.**: change in presence or absence of bleeding after gently run on the surface of the marginal gingiva.

Change in R.E.C.: change in gingival reduction.

Change in C.A.L. change in clinical attachment level.

Sample size determination

We assumed that count of sites with plaque within patient can be described by a Poisson distribution. Assuming a fixed number of sites per patient (N=48) we can model the data using a Poisson-rate model and therefore estimate the number of patients needed to achieve approximately 10% reduction (as a difference between rates) in the P.I. rate between the two treatments, corresponding to approximately 30% proportional reduction. For simplicity we considered only the effect at the latest time point. The we simulated Poisson counts for a set of candidate sample size assuming a drop from a 25% rate (12/48) to 17% (8/48) and modelled the data using a Poisson regression (GLM with Poisson family). We performed the simulation 500 times and computed the proportion of time the coefficient for the two group comparison had a p-value lower than 5%. A sample size of 16 for each groups allowed a power of at least 90%.

Statistical Analysis Plan

Data will be aggregated within patient to compute the number of site with plaque over the total number of probed sites (i.e. P.I.). Counts will be modelled using a Poisson rate model (GLMM with Poisson family) and setting the total number of site per patient as offset. A significance level of 5% will be used and all the analysis will be performed using the software R.

Randomization

Patients will be randomized to either treatment using a computer generated sequence based on a blocked randomization procedure. The software used will be R.

Summary of the procedures:

Baseline:

- clinical measurements: PPD, PI, GI, REC, CAL.
- FM-EPAPT
- randomization
- education and motivation
- 2/4 weeks:
- education and motivation
- checking compliance
- GI and PI

6 weeks:

- education and motivation
- checking compliance
- clinical measurements: PPD, PI, GI, REC, CAL.

6/12 months:

- clinical measurements: PPD, PI, GI, REC, CAL.
- FM-EPAPT
- checking compliance
- education and motivation

Drop-outs:

All drop-outs should be reported and the reason for dropping out should be investigated and reported per study group.

Publication plan:

2, 6 and 12 months results

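### Examiner calibration covers PPD and PAL only, so scoring consistency is never checked for PI, the primary outcome, or GI, the first secondary

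*Protocol*

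**What the plan says.** The Examiner calibration paragraph reads: "The examiner should be calibrated measuring PPD and PAL in one quadrant with at least 6 teeth on 10 patients". It continues: "Measurements should be repeated after one hour and variability should be assessed". No other text in the protocol deals with examiner reliability.

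The outcomes lie elsewhere. The Aim names the gingival index and the plaque index. The primary outcome is the change in PI, described as "change in 10% of the site in test group", and under Intervention PI is "recorded as presence or absence of plaque" with a probe run over the tooth surface. The first secondary outcome is GI: "change in presence or absence of bleeding after gently run on the surface of the marginal gingiva". REC and CAL follow. PPD is not listed as an outcome, though a depth above 4 mm excludes a patient.

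Probing is done "with a gentle probing force by the same examiner". At 2 and 4 weeks only GI and PI are collected.

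**The concern.** The protocol accepts that its examiner's repeatability needs checking and sets aside a session for it. It then aims that session at measures that do not decide the trial. Millimetre readings of depth and attachment say little about whether the same person calls plaque or bleeding present at the same site twice, because these are different kinds of judgement. If the calibration is carried out exactly as written, the report will hold no evidence on how consistently the primary outcome was scored. A null result for PI could then not be told apart from one blurred by inconsistent scoring.

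This is not a detail that belongs in a statistical analysis plan. Calibration is a conduct procedure, and the protocol itself fixes which measures it covers.

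**Working it through.** **1. Calibration set against use.**

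| Measure | Scale | Role in the protocol | Calibrated? |
|---|---|---|---|
| PI | yes/no per site | primary outcome; all visits | no |
| GI | yes/no per site | first secondary; all visits | no |
| REC | mm | secondary | no |
| CAL | mm | last-listed secondary | only if PAL means CAL |
| PPD | mm | exclusion criterion | yes |

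The two indices named in the Aim are both uncalibrated. At 2 and 4 weeks every examiner measurement is an uncalibrated one.

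**2. The protocol's own power figure.** Sample size determination gives 48 sites per patient, 12/48 (25%) against 8/48 (17%), 16 per group, a 5% level and power of at least 90%. I take the test as two-sided, since the protocol does not say.

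Formula: power = Φ( |ln(m1/m2)| / SE − 1.96 ), with SE = √(1/(n·m1) + 1/(n·m2)).

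With n = 16, m1 = 12 and m2 = 8:
- ln(1.5) = 0.4055
- SE = √(1/192 + 1/128) = 0.1141
- 0.4055/0.1141 = 3.553, and Φ(3.553 − 1.96) = 0.944

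A simulation of 200,000 replicates gives 0.950. The protocol's figure is reproduced. Power first reaches 90% at 14 per group (0.914; at 13 it is 0.893), so the margin is two patients per group.

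**3. Illustration of scoring error.** If p is the true site rate, the scored rate is q = sens·p + (1 − spec)·(1 − p). With equal error in both arms, the difference is multiplied by (sens + spec − 1). The true difference is 25% − 16.67% = 8.33 points. Sensitivity and specificity are my assumptions, because the protocol gives none.

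| Sens/spec (assumed) | Scored rates | Difference, points | Power at 16 per group | n per group for 90% |
|---|---|---|---|---|
| 1.00/1.00 | 25.0% vs 16.7% | 8.3 | 94% | 14 |
| 0.95/0.95 | 27.5% vs 20.0% | 7.5 | 85% | 19 |
| 0.90/0.90 | 30.0% vs 23.3% | 6.7 | 71% | 27 |
| 0.85/0.85 | 32.5% vs 26.7% | 5.8 | 56% | 39 |

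Worked row, 0.90/0.90:
- q1 = 0.90 × 0.25 + 0.10 × 0.75 = 0.300
- q2 = 0.90 × 0.1667 + 0.10 × 0.8333 = 0.2333
- expected counts per patient are 14.4 and 11.2
- ln(14.4/11.2) = 0.2513, SE = 0.0996, and Φ(2.523 − 1.96) = 0.713

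**The case against.** Several counter-arguments have force.

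- **One examiner does all the probing.** This removes between-examiner error. It leaves within-examiner inconsistency, which is what a one-hour repeat is meant to detect. The point stands, restricted to that component.
- **The choice of measures may be deliberate.** Depth and attachment suit a one-hour repeat. Running a probe over plaque or along the gingival margin can alter what the second pass sees. That is a good reason to adapt the repeat design, but not to leave the primary outcome unchecked.
- **The existing exercise is useful.** PPD decides an exclusion, and it shares the pocket base with CAL. If PAL means CAL, a secondary outcome is covered and the term is only a labelling slip. This is accepted.
- **The power table does not measure the gap.** A reader might infer that omitting PI from calibration costs this trial 9 to 38 points of power (94% down to 85% or 56%). The document does not support that. Agreement data from 10 patients change neither the site rates nor the sample size. Moreover, the 25% and 17% are PI rates, which the protocol defines as scored sites over probed sites. They may already contain scoring error, in which case power stays near 94%.
- **Direction of bias.** A reader might also infer that the PI difference is necessarily pulled toward zero. That holds only if the error is the same in both arms. The protocol calls the trial single blinded without saying who is blinded, so it cannot be taken as given.

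**Conclusion.** The point holds as a gap in the stated procedure: intra-examiner consistency is checked for an eligibility measure and, presumably, for one secondary outcome, but not for the primary outcome or the first secondary. This rests on the text alone and needs no assumption beyond reading PAL as CAL.

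Its size in terms of bias or power is unknown. The power range of 85% to 56% is an illustration. It depends on assumed sensitivity and specificity, on the planning rates being error-free, and on non-differential error. The stated sample size is not wrong on its own inputs.

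Nor should it be inferred that a repeat exercise would show how far PI is attenuated. An examiner who misses the same plaque twice agrees perfectly with himself or herself and is still inaccurate. The matter is worth correcting because the session is already planned and the correction is cheap. It does not undermine the design.

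**What to change.** Amend the Examiner calibration paragraph as follows.

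1. In the same 10 patients, also score PI and GI, before any pocket probing.
2. Define a repeat design suited to measures that the first pass can disturb, stating the interval and the order of scoring, instead of carrying over the one-hour repeat unexamined.
3. Set a site-level agreement criterion in advance, for example a minimum kappa for each index. Require recalibration if it is not met, and completion before the first patient is enrolled. Without such a criterion the exercise cannot affect how the outcome is scored.
4. Report the agreement together with patient-level repeatability of PI.
5. Replace PAL with CAL, or define PAL if something else is meant.
6. State that the exercise shows consistency and not accuracy, and that agreement may be lowered by disturbance of plaque or bleeding, or raised by examiner recall. It should therefore not be described as a lower bound.

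The cost is a few extra minutes in a session already planned, with no additional patients or examiner. The downside is that the repeat for PI and GI will be imperfect.

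### The primary outcome line names one arm, no comparator and no visit, and writes a target effect into the definition; the 12-month comparison between arms has to be inferred from other sections

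*Protocol*

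**What the plan says.** - **Primary outcome (end of Intervention).** After the label for change in PI, the whole definition is "change in 10% of the site in test group".
- **Aim.** The objective is to "compare two methods (manual VS sonic) of tooth brushing" by their impact on gingival and plaque indices "after one session of Full Mouth-Erythritol Powder Air Polishing Therapy".
- **Visits (Intervention; Summary of the procedures).** PI is recorded at baseline, at 2, 4 and 6 weeks, and at 6 and 12 months. That makes five follow-up readings. The Intervention section adds that "at 6 and 12 months professional hygiene will be done", and the summary lists that hygiene as FM-EPAPT.
- **Sample size determination.** The target is "approximately 10% reduction (as a difference between rates) in the P.I. rate between the two treatments", simulated as 12/48 against 8/48. Power is the share of runs in which "the coefficient for the two group comparison had a p-value lower than 5" per cent. On timing it says only: "For simplicity we considered only the effect at the latest time point".
- **Statistical Analysis Plan section.** A Poisson rate model with a mixed-model structure, the number of sites as offset, and a 5% level. It names no visit and no contrast.
- **Publication plan.** Results at 2, 6 and 12 months, none marked as primary.

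**The concern.** A primary outcome has to fix what is measured, between whom, and when. This line fixes only the first. It also carries a 10% figure that belongs to the sample size argument and is not part of a measurement.

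The missing visit matters most. With five follow-up readings and no declared primary one, whoever writes the report can choose the visit after seeing the data, and a nominal 5% test then no longer has a 5% error rate. The missing comparator matters less, because other sections supply it. It should still be corrected: both arms receive air polishing, instruction and reinforcement, so only the difference between arms speaks to the brush.

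**Working it through.** **1. The protocol's own power figure.** Inputs from Sample size determination: 16 per group, 48 sites, means 12 and 8, 5% level. Two-sided testing is assumed, as the protocol does not state it.

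- SE of log rate ratio = √(1/(16×12) + 1/(16×8)) = √(0.00521 + 0.00781) = 0.114
- ln(12/8) = 0.405, and 0.405/0.114 = 3.55
- Power = Φ(3.55 − 1.96) = Φ(1.59) ≈ 0.944

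This agrees with the stated power of at least 90%; 20,000 simulated trials gave 94.8%. The sizing is therefore a between-arm contrast at a single visit, and it reproduces as such. It assumes Poisson variance, that is, an SD of √12/48 = 7.2 points at a 25% rate.

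**2. The target figure.** 12/48 − 8/48 = 4/48 = 8.3 points, and 4/12 = 33% relative. The 10% in the outcome line is a rounded form of this. The simulated rates are given openly in the sample size section.

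**3. What points to a visit.**

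| Place | What it implies |
|---|---|
| Title (evidently meant as a 12-month trial) | 12 months |
| Trial design: one-year duration | 12 months |
| Sample size: last time point, as a simplification | 12 months, for sizing only |
| Primary outcome line | nothing |
| Statistical Analysis Plan section | nothing |
| Publication plan | three times, none primary |

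Where a visit is implied it is 12 months, but nowhere is it declared.

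**4. Illustrative cost of an open visit.** Suppose there is no brush effect, each visit is tested separately at two-sided 5%, and the k test statistics are normal with common correlation ρ. The protocol gives no value for ρ, so a range is assumed. Then

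P(at least one p<0.05) = 1 − ∫ φ(u) [Φ((1.96 − √ρ·u)/√(1−ρ)) − Φ((−1.96 − √ρ·u)/√(1−ρ))]^k du

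| ρ (assumed) | 3 reporting times | 5 visits |
|---|---|---|
| 0.3 | 13.6% | 20.9% |
| 0.5 | 12.5% | 18.3% |
| 0.7 | 10.9% | 14.8% |
| 0.9 | 8.4% | 10.2% |

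One named visit gives 5%.

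**5. Change or level.** The outcome line speaks of change, while the sizing simulates counts at one visit. If unadjusted change were analysed, with Poisson variances and an assumed baseline of 12/48 in both arms, the variance of change would be 24 − 24ρ in the manual arm and 20 − 2ρ√96 in the sonic arm. Here ρ is the correlation between baseline and follow-up. Power at 16 per group is Φ(4/√(sum of variances/16) − 1.96): 67% at ρ = 0, 82% at 0.3, 92% at 0.5 and 99% at 0.7. The stated power therefore belongs to PI at the visit, not to raw change.

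**6. Sessions before the 12-month reading.** The summary lists FM-EPAPT at baseline, 6 and 12 months, with measurements listed first at the last two. On that schedule the 12-month PI follows two sessions, in both arms.

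**The case against.** The strongest reply is that nobody would be misled. The title, the Aim and the sizing all describe sonic against manual, and every hint about timing points to 12 months. Most of this stands, and it rules out several stronger readings.

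- **A test within the sonic arm.** A reader might infer this from the outcome line. No such test is planned anywhere, and the sizing is explicitly a two-group comparison.
- **A contradiction over the visit.** One might read the Aim's single session as requiring a reading no later than 6 months. But the Aim names no visit, and the baseline session can be read simply as the start of follow-up, since brushes are handed out after it. The order of measurement and polishing at 6 months is also not firmly fixed, because the summary's lists are not reliably chronological. What remains is a wording mismatch: the 12-month reading follows a repeat session.
- **An actual error rate of 15–21%.** That would need separate tests and free choice among all five visits. The protocol plans one model and lists three reporting times.
- **A wrong sample size.** The gap between 10 and 8.3 points lies within the protocol's stated approximation, and the simulated rates are given.

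Model terms beyond the contrast may properly sit in a statistical analysis plan that is not shown. None of this supplies a declared primary visit. The one sentence about timing is offered as a simplification for sizing, so it does not bind the analysis.

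**Conclusion.** The point holds as a badly fixed definition that should be corrected. The outcome line omits the comparator and the visit and contains a target effect, and no other section declares the visit. The intended contrast can be inferred with fair confidence as sonic against manual at 12 months, so neither the design nor the planned model is called into question.

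The size of the problem depends on how freely the visit could be chosen: 5% if 12 months is held to, about 11–14% over three reporting times, and 15–21% over five visits at correlations of 0.7 to 0.3 (10% for five visits at 0.9). These are illustrative upper cases that rest on assumed correlations and separate tests; they do not estimate this trial's error rate.

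The sample size is unaffected: about 94% power at 16 per group, if counts have Poisson variance. Naming the visit does not by itself cure overdispersion, and with wider spread between patients power would be lower.

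**What to change.** Replace the outcome line with:

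> Primary outcome: plaque index at 12 months, compared between the sonic and manual groups as a rate ratio from the planned Poisson model with site offset, adjusted for baseline PI. PI at other visits is secondary.

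Then:

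- State that this replaces unadjusted change from baseline, so that the altered measure is visible to readers.
- Keep the target effect in the sample size section only, where 12/48 against 8/48 already stands (8.3 points, 33% relative).
- Reconcile the Aim's mention of one session with the repeat FM-EPAPT listed at 6 months. This is a matter of wording; the treatment and visit schedule is not in question here.

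**Cost.** One outcome sentence and an edit to the Aim. Sample size, randomization, visits and model family stay as they are, and baseline PI is already collected. The consent paragraph before Intervention rules out design changes after ethics approval. The revision should therefore go through as a documented amendment to the outcome wording, dated before outcome data are examined.

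### The 90% power for 16 per group was simulated with a plain Poisson GLM and one plaque rate per arm; it is not shown to hold for the planned Poisson GLMM

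*Protocol*

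**What the plan says.** Three statements in the protocol have to fit together.

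- **Sample size determination.** Counts of plaque sites per patient are taken as Poisson: "Assuming a fixed number of sites per patient (N=48"). The simulated rates are 12/48 in one arm and 8/48 in the other. The authors "modelled the data using a Poisson regression (GLM with Poisson family"), repeated this 500 times, counted p-values below 5%, and conclude: "A sample size of 16 for each groups allowed a power of at least 90" per cent. One simplification is declared: "For simplicity we considered only the effect at the latest time point".
- **Statistical Analysis Plan (section of the protocol).** The plaque index is the "number of site with plaque over the total number of probed sites". "Counts will be modelled using a Poisson rate model (GLMM with Poisson family"), with the patient's total number of sites as offset. The random effects are not named.
- **Intervention.** "A PCP-UNC 15 periodontal probe is used on six sites per tooth". Plaque is recorded at baseline, 2 weeks and 4 weeks, and again later: "Furthermore, all patients are recalled at 6 weeks 6 and 12 months". That makes five post-baseline visits. The inclusion criteria ask for about five teeth in each quadrant; I read the loosely worded criterion as a minimum.

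**The concern.** Drawing Poisson counts at one rate per arm means that all patients in an arm share the same true plaque rate, so the between-patient variance is zero. A GLMM exists to allow for patients who differ. Considering only the last visit explains why the repeated visits were left out. It does not explain the missing between-patient variance, which matters at a single visit too.

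The site count differs as well, in the trial's favour. At six sites per tooth, 48 sites are 8 teeth, whereas five teeth in each of four quadrants give 6 × 5 × 4 = 120.

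At stake is the power statement alone. Someone judging a null result from 32 patients would take it as the power of the analysis that was run. The test, the estimates and the conduct of the trial are untouched.

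**Working it through.** **Inputs from the protocol:** 16 per group; rates 12/48 and 8/48, so a rate ratio of 1.5 and ln 1.5 = 0.4055; 48 fixed sites; 5% level, taken as two-sided.

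**Assumed, because the protocol does not give it:** the between-patient SD, in points around a 25% index, with the same relative SD in the other arm (CV = SD/25).

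**1. The protocol's own figure.** SE = √[(1/12 + 1/8)/16] = 0.114; z = 0.4055/0.114 = 3.55; power = Φ(3.55 − 1.96) = 94.4%. A simulation of 100,000 plain GLM tests gave 94.9%. The stated figure is correct for that model. At 120 sites the expected counts are 30 and 20, SE = √[(1/30 + 1/20)/16] = 0.072, and power exceeds 99.9%.

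**2. Single-visit GLMM with a patient random effect.** For m sites, the variance of the log rate ratio is [1/(0.25m) + 1/(0.167m) + 2 ln(1 + CV²)]/16. Example with m = 48 and SD 8: CV = 0.32 and ln(1.1024) = 0.0975, so the variance is (0.2083 + 0.1950)/16 = 0.0252, SE 0.159, power Φ(2.55 − 1.96) = 72%. The simulated column comes from fitted GLMMs (maximum likelihood, Wald test, 2,500 runs per setting), with Poisson-lognormal / binomial-beta data.

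| Sites | SD (points) | Formula | Simulated |
|---|---|---|---|
| 48 | 5 | 86% | 86.9 / 91.3% |
| 48 | 8 | 72% | 74.0 / 78.6% |
| 48 | 10 | 63% | 65.1 / 65.8% |
| 120 | 5 | 98% | 98.3 / 98.6% |
| 120 | 7 | 92% | 91.9 / 92.6% |
| 120 | 8 | 87% | 87.1 / 87.3% |
| 120 | 10 | 75% | 75.8 / 72.1% |

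Replacing the Poisson within-patient variance by the binomial one raises the formula values to 91, 77 and 66% at 48 sites, and to 89% at 120 sites with SD 8.

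**3. Largest SD that keeps 90%.** The bracket may not exceed 16 × (0.4055/3.2415)² = 0.250.

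- 48 sites: ln(1 + CV²) = (0.250 − 0.208)/2 = 0.021, so SD = 3.6 points (5.1 with binomial variance).
- 120 sites: (0.250 − 0.083)/2 = 0.0835, so SD = 7.4 points (7.6 binomial).
- Average of five post-baseline visits (5m sites, shared patient effect): about 8.2–8.8 points.

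**4. Baseline-to-12-month contrast (group by visit, shared patient intercept).** The intercept cancels and the SD drops out. The variance is the sum of the reciprocals of the four arm totals. With an assumed baseline index of 40% and 120 sites it is (2/48 + 1/30 + 1/20)/16 = 0.0078, power 99.6%. With a 25% baseline, power is 98.7%. At 48 sites the formula gives 75% (baseline 25%) and 83% (baseline 40%); simulation gave 75–87%.

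**5. The same contrast when patients also vary from visit to visit and this is modelled.** Add 4 ln(1 + CV²)(1 − ρ)/16, where ρ is the assumed between-visit correlation. At 120 sites and baseline 40%, power for ρ = 0.8 / 0.5 is 95% / 82% at SD 8 and 91% / 70% at SD 10.

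**6. Baseline plaque index as a covariate.** With k = ln(1 + CV²), 120 sites and baseline 40%, the bracket in step 2 falls by 2(ρk)²/(k + 1/48). For ρ = 0.5 to 0.8 the formula gives 91–97% at SD 8 and 82–94% at SD 10.

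**7. Would analysing with the plain GLM remove the problem?** No. With both arms at 25%, its true SE exceeds the nominal one by the factor √[1 + 0.25m ln(1 + CV²)]. At 48 sites that is √(1 + 12 × 0.0392) = 1.21 for SD 5, a type I error of about 11%. For SD 8 it is √(1 + 12 × 0.0975) = 1.47, about 18%.

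**The case against.** The best defence is that nothing stated is false. The protocol describes its simulation openly, the 90% is true of that simulation, and the GLMM is named in the next paragraph, so a reader can see both models. The form of the random effects is often left to a separate analysis plan, which may exist. The lowest figures above use 48 sites, which the protocol's own examination rule makes too few; at 120 sites 90% survives an SD of about 30% of the mean. Under one plausible GLMM (step 4) the between-patient SD has no effect at all. Every figure below 90% rests on an SD, a baseline level or a correlation that the protocol does not supply.

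Most of this stands. The site count does offset much of the omitted variance, and no shortfall can be proven. What fails is the inference that nothing needs correcting. The power figure, the simulated model and the analysis model all stand in this document, so their mismatch is not detail deferred elsewhere. The declared simplification covers neither the zero variance nor the 48 sites. That the answer falls on either side of 90%, depending on the form of the GLMM and the SD, is the reason an unconditional figure is unsupported.

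**Conclusion.** The concern holds, as a minor point. The 90% is correct for a plain Poisson GLM with one rate per arm and 48 sites (94.4%), but it is not shown to be a property of the planned GLMM.

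The planned analysis could have clearly less than 90% (single visit, SD 8: 72–79% at 48 sites, 86–89% at 120) or clearly more (about 99% for a change from baseline at 120 sites with a purely shared patient intercept). Which applies depends on the between-patient SD, the sites actually probed, and the visits and random effects in the model. The SDs, baseline levels and correlations used here are assumptions, and 120 sites rests on reading the tooth criterion as a minimum. The mismatch itself depends on none of them.

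**What to change.** Re-run the simulation with the GLMM that will be fitted: its actual visits, random effects and offset, and the baseline plaque index if it is to be included. Use the number of sites actually probed and a stated range of between-patient SD. Then replace the unconditional power sentence with one of this form:

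> With 16 per group and [number] probed sites, the planned GLMM has [x]–[y]% power for a between-patient SD of [a]–[b] points, and at least 90% up to an SD of [c] points.

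The figures in this review illustrate the dependence and should not be entered as the protocol's power.

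The cost is one re-run of a short R simulation and one reworded sentence. The drawback is that the stated power becomes conditional on an assumed SD. Enrolment, test and conduct stay as they are.
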